MHRA	Medicine and Healthcare Products Regulatory Agency
NHS	National Health Service
NICTU	Northern Ireland Clinical Trials Unit
PI	Principal investigator
PCR	Polymerase chain reaction
POC	Point of care
PSSRU	Personal Social Services Research Unit
REC	Research Ethics Committee
RMP	Registered Medical Practitioner
ROC	Receiver operator characteristic
SDV	Source data verification
SOFA	Sequential Organ Failure Assessment
SOP	Standard operating procedure
SSC	Surviving Sepsis Campaign
STARD	Standards for Reporting of Diagnostic Accuracy
TMF	Trial Master File
TMG	Trial Management Group
TSC	Trial Steering Committee
UK	United Kingdom

1 STUDY SUMMARY

Protocol Title	Point Of Care Testing For Sepsis In ICU Patients: A Diagnostic Accuracy Study
Health condition(s) or problem(s) studied	Sepsis
Study Design	A prospective, observational, multi-centre blinded accuracy study of a novel diagnostic.
Study Aim and Objectives	
Aim To assess the diagnostic accuracy of the Randox point of care (POC) multiplex polymerase chain reaction (Multiplex PCR) test in critically ill patients with suspected sepsis.
 
Primary Objective:
 
The primary objective of this study is measurement of the sensitivity, specificity, positive predictive value and negative predictive value of this novel test, in comparison with conventional culture, in critically ill adults with suspected sepsis.
 
Secondary Objective:
 
The secondary objectives of this study are:
 
(i) to estimate the true cost per test for conventional blood culture and for multiplex PCR
 
(ii) to estimate the time to result for conventional blood culture and for multiplex PCR

Primary Outcome	The primary outcome measure is diagnostic accuracy of the multiplex PCR test for sepsis in ICU patients, expressed as sensitivity, specificity, and positive and negative predictive values, with uncertainty expressed using 95% confidence limits.
Secondary Outcomes	
Secondary outcome measures of the study are based on:
 
(i) economic measures;
 
(ii) evaluation of the primary outcome measure as when multiplex PCR testing is conducted at the point of care (vs. centrally); and

	(iii) the time to result for both the PCR test and its paired blood culture.
Inclusion and Exclusion Criteria	
Inclusion criteria:
 
 1. Patients with suspected sepsis undergoing blood sampling for culture in the course of routine care. 
Exclusion criteria:
 
 1. Patients aged <16 years old. 2. Patients previously recruited to the study. 3. Consent declined.
Countries of Recruitment	United Kingdom
Study Setting	Adult intensive care units (ICU)
Target Sample Size	4501 samples
Study Duration	21 months

STUDY TEAM

Co - Chief Investigators	
[name] Consultant Medical Microbiologist [name]
 
[name] Professor of Intensive Care Medicine Centre for Infection and Immunity Wellcome-Wolfson Institute for Experimental Medicine Queen's University Belfast [name]

3. BACKGROUND AND RATIONALE

3.1 Lay Summary

Sepsis is the term used to describe serious infections. Up to half of hospitalised patients with sepsis may die. It is caused by microbes, such as bacteria, and one of the most important things in treating patients with sepsis is to give them the right antibiotics as soon as possible to treat the underlying infection.

Many different microbes can cause sepsis. Currently the only way to find out for sure which one to target in any particular patient is to wait for it to grow in a laboratory from a sample of their blood, or other samples. As it takes at least 24-48 hours to grow in the laboratory, doctors choose 'best guess' antibiotics that can treat a lot of different microbes before they know which one would be the best fit. These are not always the right antibiotics for that particular individual, and sometimes patients only get the right treatment once there is a result from the laboratory.

Radox Ltd has recently developed a new bedside device based on technology that is able to identify bacteria in patients' blood within just one hour. Looking only for characteristic fragments of over 40 different microbes means that doctors' decisions about which treatment to give patients will not need to wait for over a day for the microbe to grow in a laboratory. This will allow treatments to be better targeted from a much earlier stage.

We will evaluate the new test in at least 15 intensive care units (ICUs) across the UK and on 4501 blood samples from patients. Whenever a blood sample is taken for culture as part of routine care, a sample will also be taken for analysis with the new test. An additional sample will also be taken for research to develop future tests. Results will be compared to the laboratory culture each time.

3.2 Background Information

3.2.1 Sepsis Management

The current internationally agreed definition of sepsis relies on the suspicion of infection in the context of a systemic inflammatory host response for which there may otherwise be many causes¹. Microbiological evidence is, therefore, crucial in confirming sepsis in the critically ill where the diagnosis is otherwise difficult to discern, while rapid decision making and intervention too is important. More than 35% of patients in European ICUs are admitted with, or develop, sepsis² and the incidence of sepsis is increasing worldwide³. The mortality of severe sepsis is consistently reported around 35% with upper estimates of 50%^{2,4-6}. In the UK, sepsis has been estimated to account for between 36,000 and 64,000 deaths annually⁴ - more than those caused by breast, colorectal and prostate cancer combined – and represents 46% of all intensive care bed-days⁷. Delay in the diagnosis of sepsis is one of the major barriers to the timely implementation of treatments and, consequently, optimal outcomes for patients with this condition⁸.

The Surviving Sepsis Campaign (SSC) and the consortium of 30 organisations 2004-2012⁹⁻¹¹, has delivered international guidelines on the management of sepsis that utilise a bundle approach and emphasise early intervention given the wealth of evidence for its clinical importance. The time to appropriate antibiotics is the single greatest predictor of survival in septic shock¹². Studies have repeatedly demonstrated an increase in mortality in both septic shock¹³ and severe sepsis¹⁴ when antibiotics are delayed beyond even just one hour; with an increase of 7.6% each hour shown in one cohort study¹⁵.

The concept of a 'golden hour' of assessment and intervention, initially described in other clinical settings, is therefore now well established in sepsis management¹². In SSC guidelines, both blood culturing and the administration of broad-spectrum empirical antibiotic treatment are recommended in the first hour after the recognition of potential sepsis. A 2010 review of the implementation of SSC guidelines across two continents demonstrated a 5.4% improvement in mortality even with only limited compliance¹⁶ although several studies also show that the empirical antibiotics received by 20-40% of patients in ICU are found to be inappropriate when the pathogen is later identified^{13,17}. Therefore, a rapid test for pathogen identification offers the opportunity to improve patients' treatment and outcomes.

Microbiological sampling in sepsis is independently associated with patients' survival¹⁸ and the SSC recommends at least two samples for traditional culture prior to the administration of antibiotics, within the first hour¹¹. Evidence on the sensitivity of blood cultures is conflicting¹⁹. The value certainly varies with the pathogen, but it is well accepted that it only approaches 100% by increasing the number of samples taken²⁰.

The emergence of multi drug resistant pathogens has gone from concerning case report to a challenging global priority over recent years- with particular relevance and incidence in intensive care settings worldwide^{21,22}. Empirical antibiotics contribute to resistance²³⁻²⁵ but remain essential to management with existing microbiological techniques that cannot provide a point of care result to identify a pathogen and guide more appropriate prescription²⁶. There is agreement that current diagnostic tools for sepsis are inadequate²⁷. The clinical need is clear: new, rapid, diagnostic methods that will facilitate prompt treatment with, effective, antibiotic therapy. To have an impact on patient management and outcomes, a novel diagnostic test in sepsis is required to be truly point of care, to provide ease of use, economy and portability, with a time to result of less than one hour.

3.2.2 Multiplex Polymerase Chain Reaction (Multiplex PCR) in Sepsis

For several years, researchers and clinicians have recognised microarray PCR as a promising technique for the rapid identification of sepsis pathogens²⁸. PCR techniques have revolutionised diagnostics in infectious diseases, particularly for viral infections, since their widespread deployment in clinical laboratories²⁹. There has been limited extension of this technology to detection of bacterial infections in routine practice, though technical progress and limited clinical evaluations have been undertaken³⁰⁻³³.

One observational study across 9 ICU units and 529 patients showed that a novel laboratory-based device (combining PCR with electro spray ionisation mass spectroscopy) could improve the diagnostic yield of microbiological sampling up to threefold compared to conventional culture and potentially identify a large number of pathogens within 8 hours³⁴.

Time to pathogen detection has been related to the length of hospital stay³⁵. POC testing may further impact the time to result. Multiplex PCR has the potential to reduce the risk of initial antibiotic treatment being inadequate³⁶. It is plausible, therefore, that benefits from adopting this technology may be both clinical and financial. Earlier analyses have predicted an absolute mortality reduction of 2.6% with the introduction of PCR techniques, and modelled that costs would be readily recovered through the savings that might be made in a setting such as intensive care¹⁷. Therefore, there is an opportunity to address this need, of particular importance in the setting of sepsis, and at the point of care.

3.3 Rationale for the Study

Best practice in sepsis is currently centred around the empirical treatment of patients pending definitive laboratory results which are available around 48 hours later. Delay in prescribing antibiotics that are appropriate for the pathogen causing a given patient's infection is associated with increased mortality and other adverse outcomes for patient.

The optimal management of sepsis is therefore still limited by the time it takes to accurately identify a causative organism. No significant progress for culture-based diagnostics has been implemented for decades.

The introduction of Multiplex PCR has been cited for several years as a possible solution to shortening the time to diagnosis. Multiplex PCR devices for the identification of sepsis pathogens currently show increased diagnostic yield when used to supplement conventional culture and can significantly reduce the time to a result. PCR may reduce delay in the focused management of sepsis; extrapolation from observational studies¹²⁻¹⁵ further implies potential for reduction in mortality associated with rapid diagnostic tests.

The emergence of multiply resistant pathogens and the need for improved antimicrobial stewardship are major healthcare issues. Empirical use of broad-spectrum antibiotics contributes significantly to resistance in both the individual and in the population's ecology. Measures to reduce the use of broad-spectrum antibiotics wherever possible are therefore advocated worldwide.

Randox Laboratories Limited, a clinical diagnostic company based in Northern Ireland, have recently developed a point of care (POC) testing device utilising Multiplex PCR for the detection of sepsis pathogens. Point of care testing would provide a result in less time than current laboratory based multiplex PCR techniques and could genuinely advance the focused management of sepsis towards improved patient outcomes. Facilitating early and focused antibiotic therapy for critically ill patients with suspected sepsis, and reducing the use or duration of broad-spectrum antibiotics, would have beneficial consequences for both patient outcomes and antibiotic conservation.

In order to have confidence in the diagnostic accuracy of the new test, it needs to undergo validation across a range of hospital sites and a broad case mix of patients. This will enable the assessment of the accuracy, NHS deliverability and potential for impact of the test in the management of suspected sepsis.

This study will test the use of a novel POC Multiplex PCR platform by assessing its accuracy in comparison with conventional cultures.

4. STUDY AIMS AND OBJECTIVES

4.1 Research Hypothesis

The Randox POC Multiplex PCR test has high diagnostic accuracy, in comparison with conventional culture, for detecting pathogens in critically ill adults with suspected sepsis.

4.2 Study Aim

The overall aim of this study is to assess the diagnostic accuracy of the Randox POC Multiplex PCR test in critically ill adults with suspected sepsis.

4.3 Study Objectives

4.3.1 Primary Objective:

The primary objective of this study is measurement of the sensitivity, specificity, positive predictive value and negative predictive value of this novel test, in comparison with conventional culture, in critically ill adults with suspected sepsis.

4.3.2 Secondary Objectives:

The secondary objectives of this study are:

- (i) To estimate the true cost per test for conventional blood culture and for multiplex PCR
- (ii) To estimate the time to result for conventional blood culture and for multiplex PCR

5. OUTCOME MEASURES

5.1 Primary Outcome Measure

The primary outcome measure is diagnostic accuracy of the multiplex PCR test, expressed as sensitivity, specificity, and positive and negative predictive values, with uncertainty expressed using 95% confidence limits.

In the primary analysis, these will be calculated by using the paired blood culture as the reference standard (i.e. the blood culture that had been taken contemporaneously). True positivity will be defined as the PCR test detecting the same genus of organism as identified in the paired blood culture.

Acknowledging that there is no perfect reference standard for sepsis, a secondary analysis will be undertaken, using a less stringent reference standard to resolve discrepant results in a 'fair umpire' test³⁷. This will be applied when the PCR test is positive and the paired blood culture is negative. In this analysis, true positivity will be defined as either:

- (i) culture of the same genus of organism in blood or other sterile site culture within 7 days of the test sample being taken; or
- (ii) culture of the same genus of organism from a non-sterile anatomic site within 3 days of the test sample being taken which is judged, by the patient's clinical team, to represent a focus of infection.

Furthermore we will undertake analysis of the primary outcome measure when multiplex PCR testing is conducted at the point of care, vs. centrally, using both the paired blood culture and the fair umpire test. The primary outcome (diagnostic accuracy) will be re-analysed including only those samples tested at the point of care and compared to the same metrics obtained when only those samples tested centrally are included.

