9. SCHEDULE OF ASSESSMENTS AND STUDY PROCEDURES

9.1 Schedule of Assessments

All patients will be evaluated during the study and data collected at each of the following time-points. For routinely collected clinical data the NHS record will be the source document and for study specific clinical measurements the CRF will be the source document.

Baseline

- Patient Demographics (date of birth, gender)
- Date and Time of ICU admission
- Suspected Source of Sepsis
- The Acute Physiology and Chronic Health Evaluation score (APACHE II) at ICU admission

At Sampling

- Site, Date and Time of sampling
- Previous Antibiotic regimens within 3 calendar days of sampling (Yes/No)
- Determinants of SOFA Score at time of sampling

Additional Assessments

- Paired blood culture result
- Multiplex PCR result
- Date and Time Multiplex PCR test completed
- Date and Time clinical team informed of blood culture result
- Results of additional blood and other sterile anatomic site cultures taken within +/-7 days of the research blood sample for suspected sepsis will also be recorded.
- Results of cultures from non-sterile anatomic sites within +/-3 days of the research blood sample for suspected sepsis will be recorded. Whether the treating physician judged this to represent a clinically-suspected focus of infection will also be recorded.

At Discharge

- Date of critical care discharge
- Date of hospital discharge

Mortality

- Date of death (within 28 days of recruitment)

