9.2 Study Procedures

9.2.1 Blood Sampling

Blood cultures will be taken in the usual manner, for the participating study site, in the course of routine care. At the time that each blood culture is taken from an eligible patient, a 5ml sample of blood will also be collected for multiplex PCR testing. An additional 10ml sample of blood will also be collected where

- (i) it is the first sample
- (ii) research staff are available to process and store the sample

In patients meeting these criteria, and where resources permit, a further 3ml sample of blood will be taken into RNA preservation reagent (Tempus) tubes.

The research blood will be obtained from the same sampling event as the matched blood culture (i.e. from the same syringe draw); if this is not possible then research blood should be obtained by the same sampling technique (i.e. venepuncture or accessing the same vascular device).

When multiple sampling sites are being used for routine clinical blood cultures at the same time, the peripheral (venepuncture) sample is preferred for matched sampling in this study. If a peripheral sample is not being obtained in routine clinical care, then obtaining matched research and routine culture samples from a vascular access device is acceptable.

At participating sites in England, Wales and Northern Ireland, patients undergoing blood culture in the course of routine clinical care will have a research blood sample taken at the same time. The research blood sample will be stored pending informed consent/assent being obtained within 72 hours of taking the sample. No research blood samples will be tested until consent/assent for participation in this study has been obtained. In the event that consent/assent is not obtained the entire research sample will be discarded with no research tests being carried out on it.

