11. STATISTICAL CONSIDERATIONS

11.1 Sample Size

The sample size is based on:

- (i) an assumed 10% event rate for true positive results among specimens collected – this is based on pilot data collected in a single centre.
- (ii) an estimated overall test sensitivity of 90%, and specificity of 95%.
- (iii) the need to ensure that the overall test sensitivity is estimated with a high degree of precision. We have set this precision as +/-3%, at the 95% confidence level.
- (iv) the ability to assess performance of the test for detecting pathogens for which true positive results are expected as infrequently as 1 in 500 tests. We have set the precision for this as +/-20%, at the 95% confidence level
- (v) Given a 10% event rate for true positive results, a sample size that achieves the proposed degrees of precision for the sensitivity estimate will enable the specificity of the test to be measured with even greater precision.

With an assumed sensitivity of 90% with a 10% true positivity rate, in order to estimate the overall sensitivity of the test with a precision of +/-3% at the 95% confidence level, 3851 samples are required. For uncommon pathogens, with an assumed sensitivity of 90% with a 0.2% true positivity rate, in order to estimate the overall sensitivity of the test with a precision of +/-20% at the 95% confidence level, 4501 samples are required. Therefore, 4501 samples will be tested to assess the diagnostic accuracy of the test using these parameters.

The sample has not been inflated for dropouts or missing data because: (i) research sampling is not necessary after the day of enrolment; (ii) the follow-up period is very short; and (iii) the nature of ICU care presents minimal risk of attrition for follow-up.

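### A contaminated paired blood culture stays a reference positive in both accuracy analyses: discordance is adjudicated in one direction only, and no significance judgement is listed for that culture

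*Protocol*

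**What the plan says.** Protocol 5.1 sets the reference for the primary analysis: "these will be calculated by using the paired blood culture as the reference standard". A match is defined by genus: "True positivity will be defined as the PCR test detecting the same genus of organism as identified in the paired blood culture". No exception is made for an isolate thought to be a contaminant.

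The same section accepts that no reference standard for sepsis is perfect and adds a secondary, fair-umpire analysis. Its scope is limited: "This will be applied when the PCR test is positive and the paired blood culture is negative". Such a pair becomes a true positive if the same genus grew in blood or another sterile site within 7 days, or at a non-sterile site within 3 days where the clinical team judged it a focus of infection.

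Protocol 9.1 lists the paired culture result, other blood and sterile-site cultures within 7 days either side, and non-sterile-site cultures within 3 days either side. For the last of these it adds: "Whether the treating physician judged this to represent a clinically-suspected focus of infection will also be recorded". No such judgement is listed for the paired culture.

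Protocol 9.2.1 ties the two specimens together: "The research blood will be obtained from the same sampling event as the matched blood culture".

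**The concern.** The plan concedes that culture can err, then corrects only one kind of error, the infection that culture missed. The opposite error, a culture that grows an organism not causing infection, is never reviewed. If PCR finds nothing in such a sample, it is charged with a missed infection. If the contaminant entered the research tube from the same draw and PCR reports its genus, PCR is credited with a true positive. Neither classification changes in the fair-umpire analysis.

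Sensitivity rests on about 450 culture positives, so a few dozen contaminants matter. The precision target ("We have set this precision as +/-3%, at the 95% confidence level") covers sampling error only. The study summary describes the outcome as accuracy for sepsis in ICU patients, and section 4.1 as accuracy for detecting pathogens, so readers will take the figure as more than agreement with culture.

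**Working it through.** **The plan's own figures (section 11.1).** Inputs: sensitivity 90%, specificity 95%, "an assumed 10% event rate for true positive results among specimens collected", half-width 3 points overall, and half-width 20 points for pathogens at a 0.2% rate. The number of reference positives needed is z² × Se × (1 − Se) / d².

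- Overall: 1.96² × 0.90 × 0.10 / 0.03² = about 384, rounded up to 385; 385 / 0.10 = 3850 (stated: 3851).
- Rare pathogens: 1.96² × 0.90 × 0.10 / 0.20² = 8.6, rounded up to 9; 9 / 0.002 = 4500 (stated: 4501).

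Both reproduce to within one sample. With 4501 samples there are about 450 culture positives, and the half-width at 90% is 1.96 × √(0.09 / 450) = 2.8 points.

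**Where a contaminated pair goes.**

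| Paired culture | PCR | Primary analysis | Fair-umpire analysis |
|---|---|---|---|
| Contaminant only | Negative | False negative | Not reviewed: false negative |
| Contaminant only | Same genus | True positive | Not reviewed: true positive |

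**Bias.** Let f be the share of culture positives that are contaminants and q the proportion of those in which PCR reports the contaminant's genus. Neither is in the protocol; both are assumptions. True sensitivity is taken as 90%. Then

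observed sensitivity = (1 − f) × 0.90 + f × q, and bias = f × (q − 0.90).

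| q | f = 5% | f = 10% | f = 20% |
|---|---|---|---|
| 0 | 85.5% | 81.0% | 72.0% |
| 0.50 | 88.0% | 86.0% | 82.0% |
| 0.90 | 90.0% | 90.0% | 90.0% |
| 1.00 | 90.5% | 91.0% | 92.0% |

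**Break-even.** Downward bias reaches 3 points at f = 0.03 / (0.90 − q).

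| q | f | Cultures out of 450 |
|---|---|---|
| 0 | 3.3% | 15 |
| 0.25 | 4.6% | about 21 |
| 0.50 | 7.5% | about 34 |
| 0.75 | 20% | 90 |

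At q = 0.90 there is no bias. The largest upward bias in this range is 0.20 × (1.00 − 0.90) = 2 points.

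**Contaminants inside or on top of the 10%.** The protocol does not say which. If they come on top and q = 0, solving 0.09 / (0.10 + c) = 0.87 gives c = 0.34% of all samples, which is again 3.3% of culture positives.

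**Precision if contaminants are excluded.** With f = 5%, 10% and 20%, 427.5, 405 and 360 positives remain, and the half-widths are 2.8, 2.9 and 3.1 points. Little is lost.

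**Effect of recoding on specificity.** Take f = 20% and q = 0.50: 90 cultures are recoded as negative, and in 45 of them PCR matched the contaminant. There are 4501 − 450 = 4051 other negatives, with about 203 false positives at 95% specificity. Counting the 45 matches as further false positives gives (203 + 45) / (4051 + 90) = 6.0%, so specificity falls from 95.0% to 94.0%. Recoding therefore moves part of the problem to another cell unless those matches are shown separately.

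**The case against.** The strongest reply is that the primary objective (section 4.3.1) is accuracy in comparison with conventional culture. On that reading nothing is misclassified: the culture grew the organism, and PCR either agreed or did not. This stands, and it is why the primary analysis should be kept.

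A second reply is that a contaminant analysis is ordinary analysis-plan content, and section 11.5 defers additional analyses there. This stands in part. A reader might infer that contaminants cannot be identified from the data and that no analysis plan could help. The protocol does not support that. The genus of the paired isolate is needed for the primary definition, other cultures are recorded over 7 and 3 days either side, time to first positive report is recorded (9.2.3), and part of the sample is kept for discrepant results (9.2.2). The case report form itself is not shown. A rule could be built, for example a skin-commensal genus not grown in any other recorded culture. It would be an imperfect proxy, because repeat cultures exist only if taken clinically, and no later plan can supply a contemporaneous judgement that sites were not asked to record.

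A third reply is that the size is assumed. This also stands. A reader might infer that the estimate must be wrong by far more than 3 points, but that depends on both f and q. At f = 5% and q = 0.30 the bias is 0.05 × 0.60 = 3.0 points, no larger than the target. The shared draw makes higher q plausible, and that shrinks the downward bias.

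**Conclusion.** The point holds as a gap in the secondary analysis and in the listed data, not as an error in the primary definition. Under sections 5.1 and 9.1 as written, a contaminated paired culture is a reference positive in both analyses, with no listed judgement of its significance. Read as sensitivity for true bloodstream infection, the estimate can be biased by more than its 3-point precision target at modest contamination, provided PCR detects well under 90% of the contaminants. Any upward bias is small. These sizes rest on 90% true sensitivity, about 450 culture positives, and assumed values of f and q.

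**What to change.** Leave the primary analysis unchanged.

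1. In section 9.1, add one item for each positive paired culture: whether the treating team judged the isolate a contaminant. Section 6.1 already blinds clinical teams to PCR results, so no new procedure is needed.
2. In section 5.1, make the secondary analysis symmetric. Report accuracy with contaminant-only cultures treated as reference negative and, alongside, with them excluded.
3. State that PCR matches to a judged contaminant are tabulated separately. State also that the umpire step may not return such a pair to positive on the strength of the same culture. Without this, a recoded pair would meet the umpire's entry condition, and its own culture would satisfy the first criterion.

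The cost is one item on about 450 samples and one extra table. The downside is a partly subjective judgement, limited by its being made blind to PCR.

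### The fair-umpire analysis reports accuracy for PCR only; PCR's umpire sensitivity is a weak readout, and the PCR-to-culture sensitivity ratio on the same reference should be prespecified

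*Protocol*

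**What the plan says.** Section 5.1 sets the outcome for one test: "The primary outcome measure is diagnostic accuracy of the multiplex PCR test, expressed as sensitivity, specificity, and positive and negative predictive values". In the primary analysis "these will be calculated by using the paired blood culture as the reference standard", and "True positivity will be defined as the PCR test detecting the same genus of organism as identified in the paired blood culture".

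The section then accepts that culture is imperfect, and so "a secondary analysis will be undertaken, using a less stringent reference standard to resolve discrepant results". On scope it says: "This will be applied when the PCR test is positive and the paired blood culture is negative". A PCR-only result becomes a true positive if the same genus grows from blood or another sterile site within 7 days, or from a non-sterile site within 3 days and the clinical team judges that site to be a focus of infection. The only comparison planned on the umpire reference is PCR run at the bedside against PCR run centrally.

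Section 11.2 uses culture only as the reference standard. The two tests are set beside each other on cost and time to result (4.3.2, 5.2), not on accuracy. Section 9.1 records additional cultures around each research sample without restricting this to discordant samples. Section 11.5 leaves further analyses to a statistical analysis plan that is not at hand.

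**The concern.** With the paired culture as reference, culture is 100% sensitive by construction and PCR can at best equal it. Only the umpire analysis can show PCR detecting infections that culture missed. The background makes yield part of the case for such tests: these devices "currently show increased diagnostic yield when used to supplement conventional culture", and one laboratory device "could improve the diagnostic yield of microbiological sampling up to threefold compared to conventional culture".

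PCR's own umpire sensitivity shows this poorly. Each confirmed PCR-only sample is added to both numerator and denominator, so the figure barely responds. It also counts no missed infection among samples negative on both tests, because those are never adjudicated. At stake is whether the secondary analysis gives a prespecified, interpretable statement about detection by PCR relative to culture, or a sensitivity in the low nineties that looks much the same either way.

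**Working it through.** **Inputs (11.1).** 4501 samples, 10% positive, sensitivity 90%, specificity 95%. The share f of PCR-only samples that the umpire confirms is not in the protocol; it is assumed to lie anywhere from 0 to 100%.

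**The plan's own figures.** Samples = z² × Se × (1 − Se) / w², rounded up, divided by the positive rate.
- Overall: 384.15, rounded up to 385; 385 / 0.10 = 3850 (stated 3851).
- Uncommon pathogens: 8.64, rounded up to 9; 9 / 0.002 = 4500 (stated 4501).

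Both reproduce to within one sample, so the inputs are read correctly.

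**Expected table.**
- Culture-positive: 0.10 × 4501 = 450.1
- Positive on both: 0.90 × 450.1 = 405.1
- Culture-only: 450.1 − 405.1 = 45.0
- PCR-only: 0.05 × 4050.9 = 202.5
- Negative on both: 0.95 × 4050.9 = 3848.4

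**Formulas.** Let b = 202.5 f and D = 450.1 + b.
- PCR sensitivity = (405.1 + b) / D
- Culture sensitivity = 450.1 / D
- Ratio = (405.1 + b) / 450.1
- SE(log ratio) = √[(b + 45.0) / ((405.1 + b) × 450.1)]
- PCR PPV = (405.1 + b) / 607.6
- PCR specificity = 3848.4 / (4050.9 − b)

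| Confirmed share (assumed) | PCR sensitivity | Culture sensitivity | Ratio (95% CI) | PCR PPV | PCR specificity |
|---|---|---|---|---|---|
| 0% | 90.0% | 100% | 0.90 (0.87 to 0.93) | 66.7% | 95.0% |
| 20% | 90.8% | 91.7% | 0.99 (0.95 to 1.03) | 73.3% | 96.0% |
| 50% | 91.8% | 81.6% | 1.13 (1.07 to 1.18) | 83.3% | 97.4% |
| 100% | 93.1% | 69.0% | 1.35 (1.27 to 1.43) | 100% | 100% |

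The ratio equals 1 when b = 45.0, that is f = 45.0 / 202.5 = 22%.

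**Double negatives.** Take f = 50%, so b = 101.3 and D = 551.4. Suppose a share g of the 3848.4 double negatives would also meet the umpire criteria (assumed).
- g = 0: 506.4 / 551.4 = 91.8% against 450.1 / 551.4 = 81.6%.
- g = 2% (77.0 samples, D = 628.3): 80.6% against 71.6%.
- g = 5% (192.4 samples, D = 743.8): 68.1% against 60.5%.

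The ratio is 506.4 / 450.1 = 1.125 in all three, because D cancels; D does not enter its standard error either. The paired difference keeps its sign but shrinks: 10.2, 9.0 and 7.6 points.

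**The case against.** The strongest case against the point has four parts.

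1. **The information is not lost.** Section 11.2 promises 2×2 tables, and every term in the ratio can be read from the primary and umpire tables. This stands. A reader might infer that the study would be unable to say whether PCR detects fewer or more infections than culture. The documents do not support that. What is missing is a prespecified estimate with limits that allow for pairing and clustering, and clustering cannot be recovered from the tables.

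2. **Sensitivity is not the only planned output.** PPV is planned too, and moves from 66.7% to 100% over the same range. This stands, so the plan does not hide the confirmed share. PPV does not set it against the 45 infections that only culture found, however, and the ratio does.

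3. **The study question is not superiority in yield.** The hypothesis, aim and primary objective concern PCR measured against culture. The rationale rests mainly on speed, which is compared directly. The yield statement in 3.3 describes an add-on role, and the threefold figure in 3.2.2 belongs to a different, laboratory-based device. This stands. A reader might go on to say that the overall conclusion about PCR should rest on the paired contrast; the documents do not justify that.

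4. **The analysis plan may add it.** It may. But 5.1 itself fixes which samples are adjudicated, which test is scored and the one umpire comparison, so the point concerns what the protocol states.

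A further caution is that scoring culture on a reference that adjudicates one discordant cell is not fully even-handed. Culture keeps 100% specificity by construction, and both absolute sensitivities and their difference depend on the double negatives. The ratio avoids the second problem but not the first.

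**Conclusion.** The point holds as a modest, low-cost improvement to a secondary analysis. On the planning values, PCR's umpire sensitivity can vary by only about 3 points (90.0% to 93.1%), while the ratio to culture goes from clearly below 1 to clearly above it (0.90 to 1.35). The sensitivity is also overstated if any double negatives would meet the umpire criteria: with half of the PCR-only samples confirmed, 91.8% would fall to 80.6% or 68.1% if 2% or 5% of them did. The ratio is unaffected.

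This rests on the 11.1 inputs, on assumed ranges for the confirmed share and the double-negative share, and on a simple 2×2 table without genus mismatches between two positive tests. The intervals treat samples as independent. Section 7.4 lets a patient contribute several samples, so they are approximate. The primary analysis and the sample size are not called into question.

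**What to change.** Add to the secondary analysis in 5.1: 'The paired blood culture will be tabulated against the same umpire reference, and the ratio of PCR to culture sensitivity will be reported with 95% confidence limits that allow for pairing and for repeat samples per patient.'

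Report this ratio as the main umpire result on detection, alongside PCR specificity and PPV. Label absolute umpire sensitivities, and any difference between them, as dependent on unadjudicated double negatives. The alternative is to use the cultures recorded under 9.1 to apply the umpire to every sample. That needs a stated criterion for PCR-negative samples, where there is no PCR genus to match.

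The cost is protocol or analysis-plan wording and one paired table, with no new samples, data or staff. Two limits must be stated with the result: every culture-positive sample counts as true infection, contaminants included, which favours culture; and coincidental genus matches count as confirmation, which favours PCR.
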